Prior to initiating enrollment for Dose Level 4 in Group 1, an analysis of all available safety, PK, and PD data from previous cohorts will be reviewed.

If a subject is enrolled in a dose level but does not complete the PK or PD analysis, they may continue on study but an additional subject may be enrolled at that dose level.

The MTD is the highest dose level with a subject incidence of ≤ 1 DLTs during the first 28 days of study drug dosing of 6 subjects. A minimum of 6 subjects need to be treated at a dose level before this dose level can be deemed as the MTD.

Group 2: Combination therapy of GS-5829 with exemestane or fulvestrant in patients with advanced stage estrogen receptor positive breast cancer

Cohorts of subjects with advanced stage estrogen receptor positive breast cancer for whom no standard curative therapy exists and who are candidates for exemestane or fulvestrant will be sequentially enrolled at progressively higher dose levels of oral GS-5829 in combination with full standard doses of exemestane or fulvestrant. The starting dose of GS-5829 will be 2.0 mg QD, which is a dose level that has been demonstrated to be safe and tolerable (no Grade 2 or higher drug related toxicity) as a single agent in patients with solid tumors. Dose escalation will continue with cohort sizes of 3-6 subjects in parallel arms: Group 2A will initiate with 2.0 mg of GS-5829 orally once daily on Cycle 1 Day 1 combined with 25 mg of exemestane administered once daily beginning on Cycle 1 Day 1. The subject may initiate exemestane any time prior to, or on, Cycle 1 Day 1. Group 2B will initiate with 2.0 mg of GS-5829 orally once daily on Cycle 1 Day 1 with 500 mg fulvestrant administered intramuscularly (Cycle 1 Day 1 and then every 28 days (+/-3 days). If Cycle 1 Day 1 is the subject’s first dose of fulvestrant, a one-time additional dose of fulvestrant should be administered on Cycle 1 Day 15.

The candidate doses of GS-5829 for each Dose Level for Group 2 are shown in the table below.

Group 2: Combination of GS-5829 in Breast Cancer

Dose Level	GS-5829*	Group 2A Exemestane	Group 2B Fulvestrant
1	2 mg	25 mg orally once daily	500 mg intramuscularly day 1, 29 and then every 28 days**
2	3 mg		
3	4 mg		
4	6 mg		
5	9 mg		
6	12 mg		

* Dose Levels may be modified based on emerging safety and PK results.

** Subjects initiating fulvestrant on this study should receive a single additional dose of fulvestrant on Cycle 1 Day 15.

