Test Product, Dose, and Mode of Administration:	
GS-5829 tablets will be self-administered orally once daily, beginning on Cycle 1 Day 1 of the study and thereafter at approximately the same time each day until end of treatment. Subjects in the first 3 Dose Levels will be administered GS-5829 in the clinic as a single dose and then 7 days later will self-administer GS-5829 orally once daily. GS-5829 is supplied as 0.2, 1, 5, and 10 mg tablets.
 
For subjects in Group 2A, exemestane tablets will be self-administered orally once daily, beginning on Cycle 1 Day 1 of the study and thereafter at approximately the same time each day until the end of treatment.
 
For subjects in Group 2B, fulvestrant will be administered intramuscularly by the clinic staff on Cycle 1 Day 1, Cycle 1 Day 15 and Cycle 2 Day 1 of the study and thereafter at approximately every 28 days (+/- 3 days) until the end of treatment.

Reference Therapy, Dose, and Mode of Administration:	Not Applicable
Criteria for Evaluation:	
Safety:	Safety will be evaluated by assessment of clinical laboratory tests, physical examination, 12-lead ECG, vital signs measurements, and the documentation of AEs
Efficacy	Efficacy will be evaluated by overall response rate (ORR) (complete response [CR] + partial response [PR], assessed as per RECIST v1.1 or appropriate evaluation such as Cheson Criteria for lymphoma or based on the Prostate Cancer Working Group [PCWG] for prostate cancer) and progression-free survival (PFS), defined as the interval from first dose date of study drug to the earlier of the first documentation of definitive disease progression or death from any cause.
Pharmacokinetics:	The following PK parameters for GS-5829 will be calculated as applicable: C_{max} , AUC_{last} , AUC_{tau} , C_{tau} , T_{max} , and $t_{1/2}$

Statistical Methods:**Analysis Methods**

The Full Analysis Set (FAS) will be used in the analyses of subject characteristics and efficacy endpoints. The FAS consists of all subjects who receive ≥ 1 dose of study drug. A Safety Analysis Set for this study will be the same as FAS since this study is a non-randomized study. Other analysis sets (DLT-Evaluable and PK/PD analysis sets) will be used for additional analyses as well.

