4.3. Exclusion Criteria

Subjects who meet *any* of the following exclusion criteria are not to be enrolled in this study.

- 1) History or evidence of clinically significant disorder, condition, or disease that, in the opinion of the Investigator or Medical Monitor would pose a risk to subject safety or interfere with the study evaluations, procedures, or completion
- 2) Pregnant
- 3) Known brain metastasis or leptomeningeal disease

- 4) Uncontrolled intercurrent illness including, but not limited to, active uncontrolled infection, active or chronic bleeding event within 28 days prior to first dose of study drug, uncontrolled cardiac arrhythmia, or psychiatric illness/social situation that would limit compliance with study requirements as judged by treating physician
- 5) Myocardial infarction, symptomatic congestive heart failure (New York Heart Association Classification > Class II), unstable angina, or serious uncontrolled cardiac arrhythmia within the last 6 months of study Day 1
- 6) Major surgery, defined as any surgical procedure that involves general anesthesia and a significant incision (ie, larger than what is required for placement of central venous access, percutaneous feeding tube, or biopsy) within 28 days of first dose of study drug
- 7) Impairment of gastrointestinal (GI) function or GI disease that may significantly alter the absorption of GS-5829, including any unresolved nausea, vomiting, or diarrhea that is Common Terminology Criteria for Adverse Events (CTCAE) Grade >1
- 8) Minor surgical procedure(s) within 7 days of enrollment or randomization, or not yet recovered from prior minor surgery (placement of central venous access device, fine needle aspiration, or endoscopic biliary stent \geq 1 day before enrollment or randomization is acceptable)
- 9) Anti-tumor therapy (chemotherapy, antibody therapy, molecular targeted therapy) within 21 days or 5 half-lives, whichever is longer, of study drug dosing (6 weeks for nitrosoureas, mitomycin C, or molecular agents with $t_{1/2} > 10$ days); concurrent use of hormone therapy for prostate cancer is permitted, and concurrent use of exemestane or fulvestrant (and goserelin for pre/perimenopausal breast cancer as per inclusion criteria 2.c.iv) for subjects enrolled in Group 2 (advanced breast cancer) is permitted

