Faslodex[®] (fulvestrant) is supplied as 50 mg/mL for intramuscular administration. Subjects assigned to receive fulvestrant in combination with GS-5829 in this study will receive fulvestrant on Cycle 1 Day 1 and every 28 days (+/- 3 days) until the end of treatment. For subjects initiating fulvestrant on this study, a single additional dose of fulvestrant 500 mg should be administered on Cycle 1 Day 15 (+/- 3 days). Fulvestrant should be administered intramuscularly into the buttocks slowly (1 – 2 minutes per injection) as two 5mL injections, one in each buttock. Refer to [Appendix 10](#) for further details.

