- t Bone marrow biopsy is only to be performed to assess suspected CR, and only if the subject had lymphoma involvement of the marrow at baseline (or did not have a baseline marrow biopsy). After CR is determined, there is no need for any further bone marrow biopsy assessments.

- I** [REDACTED]
- v At one or more dose levels, GS-5829 will be administered in fed state on Day 1 of Cycle 2 and PK samples will be collected at pre-dose and 0.5, 1, 2, 3, 4, 6, 8, and 24 hours post-dose. In subjects where intensive PK is collected on Cycle 2, Day 1, sparse PK samples do not need to be collected at that visit.
 - w Subjects assigned to receive exemestane in combination with GS-5829 in the study will self-administer exemestane orally once daily starting on or before on Cycle 1 Day 1 and thereafter at approximately the same time each day until the end of treatment. Subjects assigned to receive fulvestrant in combination with GS-5829 in this study will receive fulvestrant 500 mg IM on Cycle 1 Day 1 and every 28 days (+/- 3 days) until the end of treatment. For subjects initiating fulvestrant on this study a single dose of fulvestrant 500 mg should be administered on Cycle 1 Day 15 (+/- 3 days).
 - x Biopsies are requested from subjects with accessible disease and should be core needle or excision biopsies. The pre-treatment biopsy can be obtained any time after the last line of therapy and prior to the first dose, the Cycle 2 Day 15 biopsy can be obtained anytime between Cycle 2 Day 1 and Cycle 2Day 21. The EOT biopsy should be collected at progression only for subjects with progressive disease.
 - y AAG will be collected at Screening, pre-dose on C1D1 and C1D8 only. Ferritin and CRP will be collected pre-dose on C1D1 and Day 1 of every subsequent cycle.
 - z Subjects who are enrolled in Group 3 will undergo a baseline PET/CT scan and at Week 16 in the place of a CT scan if available.

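### One synopsis row gives the Cycle 1 Day 15 fulvestrant dose to all of Group 2B; every other statement limits it to subjects starting fulvestrant on study

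*Protocol*

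**What the plan says.** The synopsis row covers Group 2B as a whole: "fulvestrant will be administered intramuscularly by the clinic staff on Cycle 1 Day 1, Cycle 1 Day 15 and Cycle 2 Day 1", and roughly every 28 days after that. It carries no condition and no footnote.

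The rest of the plan treats the Day 15 dose as an addition for new starters:

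- The synopsis Group 2 design text, Protocol Section 3.2 and SAP Section 1.2 make it depend on Cycle 1 Day 1 being the subject's "first dose of fulvestrant, a one-time additional dose of fulvestrant should be administered on Cycle 1 Day 15".
- The footnotes to the Group 2 dose tables (synopsis, Protocol Table 3-2, SAP Section 1.2) say: "Subjects initiating fulvestrant on this study should receive a single additional dose of fulvestrant on Cycle 1 Day 15".
- Protocol Section 5.3 says: "For subjects initiating fulvestrant on this study, a single additional dose of fulvestrant 500 mg should be administered on Cycle 1 Day 15".
- Footnote w of the schedule of procedures (Protocol Appendix 2, SAP Appendix 1) says: "For subjects initiating fulvestrant on this study a single dose of fulvestrant 500 mg should be administered on Cycle 1 Day 15".

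Exclusion criterion 9 in Protocol Section 4.3 permits "concurrent use of exemestane or fulvestrant (and goserelin for pre/perimenopausal breast cancer as per inclusion criteria 2.c.iv) for subjects enrolled in Group 2".

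**The concern.** The row tells the reader what dose to give and when, and it contradicts the rule in the body of the protocol. The contradiction would not matter if every Group 2B subject started fulvestrant on study, but criterion 9 lets in subjects already on it. The conditional wording itself presupposes such subjects.

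For a continuing subject the stakes are practical. Followed literally, the row leads to an extra dose that the design does not intend, given "as two 5mL injections, one in each buttock" according to Section 5.3. The site is also left without a compliant course. Giving the dose departs from Section 5.3 and omitting it departs from the synopsis row, while Protocol Section 6 asks investigators to document any deviation from protocol procedures.

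The statistical stakes are small. The Day 15 dose falls inside the 28-day DLT window, but the intended rule already mixes starters (two doses in Cycle 1) with continuing subjects (one dose). The slip therefore gives no basis for claiming a shift in DLT rates or a loss of comparability between cohorts.

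**Working it through.** The plan states no statistical figure on this point. The check is a comparison of every statement of the schedule, followed by a dose count.

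**Step 1. Statements of the Day 15 rule**

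| Place | Day 15 dose goes to |
|---|---|
| Synopsis, test product row | all of Group 2B |
| Synopsis, Group 2 design text | subjects whose first dose is Cycle 1 Day 1 |
| Synopsis, Group 2 table footnote | subjects starting on study |
| Protocol Section 3.2, Group 2 text | subjects whose first dose is Cycle 1 Day 1 |
| Protocol Table 3-2 footnote | subjects starting on study |
| Protocol Section 5.3 | subjects starting on study |
| Protocol Appendix 2, footnote w | subjects starting on study |
| SAP Section 1.2, Group 2 text | subjects whose first dose is Cycle 1 Day 1 |
| SAP Section 1.2, Group 2 table footnote | subjects starting on study |
| SAP Appendix 1, footnote w | subjects starting on study |

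Conditional: 6 (protocol) + 3 (SAP) = 9. Unconditional: 1.

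**Step 2. Possible second exception.** Both schedule tables mark Day 15 with an X in the exemestane or fulvestrant row, which looks unconditional on its face. That row carries footnote w, which states the condition, so the schedule agrees with the nine.

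**Step 3. Dose count.** Inputs from Section 5.3 are 500 mg per dose, 50 mg/mL, and two 5 mL injections per dose. Nominal visit days are used.

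| Subject | Period | Synopsis row | Rule elsewhere | Difference |
|---|---|---|---|---|
| Already on fulvestrant | Cycle 1 (Days 1–28) | 2 × 500 = 1,000 mg | 1 × 500 = 500 mg | 500 mg |
| Already on fulvestrant | through Cycle 2 Day 1 | 3 × 500 = 1,500 mg | 2 × 500 = 1,000 mg | 500 mg |
| Starting on study | Cycle 1 (Days 1–28) | 1,000 mg | 1,000 mg | 0 |
| Starting on study | through Cycle 2 Day 1 | 1,500 mg | 1,500 mg | 0 |

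Volume of the excess: 500 mg ÷ 50 mg/mL = 10 mL = 2 × 5 mL injections.

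**Step 4. Number affected.** The documents do not report how many Group 2B subjects were already on fulvestrant. With cohorts of three newly enrolled subjects, the possible number is 0 to 3 per cohort.

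**The case against.** The strongest reply is that this is an editorial slip whose answer the documents already supply. Section 5.3 is the operative dosing section and is conditional, as is the schedule through footnote w. The synopsis itself gives the condition twice before the reader reaches the row. Harm requires a site to follow one summary row over all of these. This stands as a limit on likelihood, but the synopsis still states both versions, and the unconditional one is in the row headed dose and administration.

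The row also compresses other rules. It has exemestane beginning on Cycle 1 Day 1, although Section 5.3 allows an earlier start. It gives the single lead-in dose to the first three dose levels without limiting this to Group 1. That pattern does suggest abbreviation and not a competing rule. It explains the error but does not make the sentence correct.

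The consequence is thin: 1,000 mg in Cycle 1 is what every new starter is meant to receive, and nothing in the documents shows that this amount harms a continuing subject. That stands, and no toxicity is claimed.

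Finally, the upper limit of 3 rests on one of two stated cohort sizes. The Group 2 text also speaks of 3 to 6 subjects, and Section 6.6 allows replacements, so the count at one dose level could be 6 or more. That also stands.

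**Conclusion.** The concern holds. The synopsis row is wrong as written, and the other nine statements agree with one another. Its size is one unintended 500 mg dose (10 mL, two injections) for each Group 2B subject already on fulvestrant at entry, and nothing for subjects starting on study. The number of such subjects is unknown: 0 to 3 per three-subject cohort, more if a dose level is enlarged or subjects are replaced.

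This is an internal inconsistency in a dosing statement. It does not touch the design, the sample size or the analysis. The dose count assumes nominal visit days and a site that follows the row literally. SAP Section 1.3 records the study as completed with 33 subjects, so a correction now cannot alter doses already given. Whether any continuing subject received the extra dose can be settled only from the dosing records.

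**What to change.** In the synopsis row, qualify the Day 15 visit so that the schedule reads: *on Cycle 1 Day 1, Cycle 1 Day 15 (only for subjects initiating fulvestrant on this study) and Cycle 2 Day 1*. No other statement of the fulvestrant rule needs to change. The cost is one phrase in one row.

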1. INTRODUCTION

1.1. Background

GS-5829 is a small-molecule inhibitor of the highly conserved bromodomain pockets of the bromodomain and extraterminal (BET) proteins. Bromodomain and extraterminal proteins regulate specific gene expression by enhancing ribonucleic acid (RNA) polymerase II (RNAPII)-mediated transcription. Signal transduction pathways recruit BET proteins to target genes through posttranslational modification of histone proteins in the form of lysine acetylation {[Belkina et al 2012](#), [Hargreaves et al 2009](#)}. The tandem bromodomain motifs of BET proteins specifically recognize acetylated histones and, in turn, recruit protein factors that regulate RNAPII {[Shi et al 2014a](#)}. The BET family includes bromodomain-containing proteins 2, 3, 4, and T (BRD2, 3, 4, and T). BRD2, 3 and 4 are widely expressed and regulate gene transcription in diverse cell types, including malignant cells, whereas BRDT expression is restricted to the testes.

[figure not shown]
BRD2, 3, 4 are essential regulators of the expression or activity of several key oncogenic transcription factors, including v-myc avian myelocytomatosis viral oncogene homolog (MYC) and the androgen receptor (AR) {[Shi et al 2014a](#)}. Transcription of the MYC gene is dependent on BET proteins in many cells {[Mertz et al 2011](#)} ([Figure 1-1](#)). Androgen receptor-dependent transcription of target genes requires BET proteins in prostate cancer cells {[Asangani et al 2014](#)}. Cancer cells addicted to MYC and AR are highly sensitive to BET protein inhibition {[Asangani et al 2014](#), [Delmore et al 2011](#), [Mertz et al 2011](#)}, which provides the basic therapeutic rationale for BET inhibition with GS-5829 for the treatment of cancer.

MYC promotes cell proliferation, cell survival, and metabolic adaptation and is frequently overexpressed in human cancers {[Dang 2012](#)}. Data generated at Gilead demonstrated MYC overexpression to be prevalent in 76% of prostate cancer (n = 60), 67% of diffuse large B-cell lymphoma (DLBCL) (n = 98), 65% of multiple myeloma (MM, n=30), 73% of colorectal cancer (n = 60), and 80% of ovarian cancer (n = 60) cases examined (PC-350-2083). These data are consistent with literature that reports a high incidence of MYC expression in these and other cancers {[Affer et al 2014](#), [Barrans et al 2010](#), [Chesi et al 2008](#), [Chng et al 2011](#), [Glitzka et al 2014](#), [Hawsworth et al 2010](#), [Nesbit et al 1999](#), [Nupponen et al 1998](#), [Perry et al 2014](#)}. The AR is a nuclear hormone receptor that is nearly ubiquitously expressed in prostate cancer (PC-350-2083) and activates growth and survival signals both by binding to androgen, its natural ligand, and through androgen-independent mechanisms {[Yuan et al 2014](#)}.

A number of orally administered, BET-directed compounds (TEN-010, CPI-0610, OTX015, ZEN-3365, and GSK525762) are currently in early-stage clinical development for the treatment of solid tumors or hematologic cancers. Initial evidence of clinical activity at tolerated doses has been reported for the BET inhibitor OTX015 in patients with refractory hematological cancers {[Herait et al 2014](#)}. GS-5829 is an orally available small-molecule inhibitor of BET proteins that is being developed by Gilead Sciences, Inc. for the treatment of solid tumors, including castrate-resistant prostate cancer (CRPC), estrogen receptor positive advanced stage breast cancer and hematologic malignancies. In nonclinical studies, GS-5829 inhibited cell growth and

induced apoptosis of solid tumor and hematological cancer cells by inhibiting BET protein-dependent transcription of MYC and other oncogenic pathways, including transcription mediated by the AR in prostate cancer cells and the ER in breast cancer cells.

Figure 1-1. Mechanism of Action of GS-5829 to Reduce Transcription of MYC and AR Target Genes in Cancer Cells

Bromodomain and extraterminal proteins, including BRD4, are recruited to the MYC promoter and enhancer elements through an interaction between the tandem bromodomains and acetylated histone proteins in chromatin (top panel). BRD4 recruits the positive transcription elongation factor b (pTEFb) complex to the MYC gene, which phosphorylates RNAPII to increase transcription of the MYC gene. GS-5829 binds to the bromodomains of BET proteins, thereby blocking the interaction with acetylated histone proteins and leading to a reduction of MYC transcription. GS-5829 similarly functions to inhibit the transcription of AR target genes in prostate cancer cells, including the kallikrein-related peptidase 3 (KLK3) gene that encodes prostate specific antigen (bottom panel).

1.2. GS-5829

1.2.1. General Information

For further information on GS-5829, refer to the current investigator's brochure for GS-5829.

1.2.2. Preclinical Pharmacology and Toxicology

1.2.2.1. Absorption, Distribution, Metabolism, and Elimination

GS-5829 shows moderate plasma protein binding and volumes of distribution in nonclinical species that are similar to or slightly higher than total body water. Systemic clear in nonclinical species is generally well predicted from the rates of metabolism by hepatocytes. Since GS-5829 has high metabolic stability with human hepatic material in vitro, it is likely to show low clearance in humans. The major route of metabolism of GS-5829 involves hydroxylation of the 5-methyl moiety on the 3,4-dimethyl isoxazole ring catalyzed primarily by CYP3A4 and CYP3A5 enzymes in humans.

Consistent with the moderate to high bioavailability seen in nonclinical species, shows high forward permeability across Caco-2 monolayers, and low efflux, but GS-5829 is a substrate of human P-g and BCRP.

GS-5829 has relatively high unbound fraction in cell culture medium containing fetal bovine serum. Competitive dialysis between cell culture median and human, dog and mouse plasma yielded a ratio of unbound fractions of 5.7, 15.2 and 13.2 respectively.

GS-5829 is unlikely to cause clinical interaction through inhibition of CYP1A2, CYP2C9, CYP2C19, or CYP2D6, CYP2B6, CYP2C8, CYP3A or UGT1A1, so the potential for causing drug interactions through inhibition of those enzymes is low. GS-5829 is also a weak inhibitor of the human efflux transporters, P-gp and BCRP, and the uptake transporters, OATP1B1 and OATP1B3.

1.2.2.2. Nonclinical Toxicology

Nonclinical safety pharmacology and toxicology studies have characterized the safety of GS-5829 through repeat dose toxicology studies. All pivotal toxicology studies were conducted in full compliance with Good Laboratory Practice regulations (21 CFR 58). The scope of the nonclinical safety evaluation is consistent with the guidance issued by the International Conference on Harmonisation (ICH).

In nonclinical pharmacology studies, GS-5829 showed no significant adverse effects on central nervous, respiratory or cardiovascular system functioning at the projected exposure and human target dose of 25 mg once daily.

The following target organs/systems were identified in the nonclinical toxicology studies: hematopoietic and male reproductive system (mice and dogs), the adrenal and skin (mice), and the gastrointestinal tract, respiratory and cardiac (dogs). With the exception of the adrenals in the mouse and the respiratory and cardiac hemorrhages observed in dogs, target organs are as expected based on the known pharmacology. The dog was the more sensitive species, with the no-observed-adverse-effect levels in the mouse and dog 10 and 0.03 mg/kg/day respectively. The severely toxic dose in 10% of mice and the highest HNSTD in dogs were 25 and 0.1 mg/kg/day, respectively.

Hematopoietic effects include decreases in white blood cells, lymphocytes, platelets and reticulocyte counts as well as mild reduced cellularity in the marrow in mice at doses of ≥ 10 mg/kg/day. Minimal to marked decrease in bone marrow cellularity, decrease in lymphocytes in the lymphoid tissues (spleen, thymus, lymph nodes and gastrointestinal associated lymphoid tissue), decrease in neutrophils and platelets were observed at 0.3 mg/kg/day in dogs. Elevated fibrinogen was also noted at the 0.3 mg/kg/day in dogs.

Mild to moderate alveolar (lung) hemorrhage was observed at ≥ 0.1 mg/kg/day in dogs. Mild hemorrhage in the left atrioventricular valve of the heart was seen at the 0.3 mg/kg/day in 1 of 6 dogs. The mechanism for the hemorrhage is not known. Protime and partial thromboplastin time measurements were normal. The anatomic pattern of the hemorrhage in the lung field and microscopy appears were considered potentially consistent with pneumonia, however bacteria were not identified.

In the male reproductive system, decreased testes weight with oligospermia/aspermia were observed in both mouse and dog studies at 25 mg and 0.3 mg/kg/day respectively. Minimal to moderate vacuolation of the seminiferous tubules occurred at ≥ 0.1 mg/kg/day in the dog. These changes are consistent with the known effects of a bromodomain inhibitor on the testes.

The gastrointestinal findings in the dog included minimal to mild mucosal atrophy, mucosal hemorrhage and crypt hyperplasia in the stomach or intestines at ≥ 0.1 mg/kg/day. Adrenal gland weight decreases were noted at 25 mg/kg/day and cytoplasmic vacuolation at ≥ 10 mg/kg/day in the mouse studies, of unknown cause. QT prolongation is not expected based on hERG, rodent and dog studies.

